4.2 Study Outcome Measures

4.2.1 Primary Outcome Measures

The primary outcomes are alcohol consumption and cravings during the alcohol self-administration trials. Drinking volume during the alcohol self-administration will be measured to evaluate the effects of exenatide vs. sham injection on the rate of alcohol consumption after a priming drink. Alcohol craving will be measured using the Visual Analog Scale (VAS) and the Alcohol Urge Questionnaire (AUQ)³⁰ during the exenatide self-administration trial. These self-report measures of craving will be used to evaluate the effect of exenatide on craving vs. placebo.

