Subjects will be given a priming drink designed to increase the subject's blood alcohol level (BAL) to 0.03g/dl, using the alcohol of their choice that is 24% Alcohol By Volume (ABV) or greater. Drinks will be mixed with a sugary mixer (3:1 Mixer:Alcohol) to preclude the occurrence of hypoglycemia. The volume of alcohol will be calculated using an online tool developed by UW-Madison (<http://dionysus.psych.wisc.edu/WebCMS/baccalc.htm>) based on a formula described by Watson⁵¹. The subjects will be asked to drink the priming drink over a period of 5 minutes. The purpose of the priming drink is to normalize drinking in the laboratory.

Absorption period. Subjects will be observed for 40 minutes following the priming dose of alcohol. This period will provide ample time for subjects to reach the target BAC. Breathalyzer readings will be completed at 10 minutes intervals.

Alcohol self-administration Blocks 1 and 2. In each of the alcohol self-administration Blocks, subjects will be presented with four drinks, each mixed to raise their BAC by 0.0125g/dl. They will be told that they can either consume the desired number of drinks over the following 60 minutes, or they will receive the equivalent dollar amount of the cost of each drink (\$3.00) they did not consume. At the end of each 1-hour session the drinks will be removed and the volume of alcohol remaining will be measured with a graduated cylinder. Cravings will be assessed using the AUQ and VAS every 30 min during the self-administration blocks. BAC levels will be obtained at the end of the Block 2 session as will blood glucose levels. Blood glucose levels will be measured at the end of Block 2 using a glucometer and blood obtained from a pinprick sample. If the subject is found to be hypoglycemic (glucose < 70 mg/dL), staff will give the subject orange juice and re-test in 30 minutes. If the subject is found to be hyperglycemic (glucose > 300 mg/dl), staff will escort the subject to the BMC emergency department for evaluation. At the end of this session subjects will also be asked to rate their experience of nausea using a visual analog scale developed to assess nausea in an emergency department⁵². Subjects will be assessed for safety prior to subjects leaving the laboratory. Subjects will not be released until their BAC is below 0.04 g/dl and they are not behaviorally impaired.

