12.1 Study Hypotheses and Planned Analyses

For our primary outcomes, data from subjects who experience moderate to severe nausea during the alcohol self-administration trials will be excluded from our statistical analysis. Although the dosing chosen for this study minimizes the potential for nausea as a medication side effect, this may occur in some subjects. These subjects will be excluded from analyses as medication-induced nausea could confound the drinking outcomes. The presence of nausea will be established by a rating greater than 30 on a VAS scale that rates nausea from no nausea to unbearable nausea⁵³.

Hypothesis	Proposed Analyses
1. Subjects will consume less alcohol during an alcohol Challenge Trial when receiving exenatide	The volume of alcohol consumed during alcohol challenge trials 1 and 2 will be used to test the effect of exenatide on alcohol consumption. We will use a mixed

The Effects of Exenatide, a GLP-1 Agonist, on Alcohol Self-Administration in Heavy Drinkers
 Version 1.8 10.5.20

compared to when they receive a sham injection.	models repeated measures approach to test for differences between alcohol consumption between the exenatide and sham injection self-administration trials ⁵⁴⁻⁵⁵ . This data will be divided into first and second-hour blocks of self-administration. Within-subject factors for this analysis will include Treatment and Time Block. Trial order will be used as covariate in these analyses to allow evaluation as to whether the order of treatments had a significant effect on the outcome. Appropriate covariance structures will be determined using Akaike's information criteria to evaluate the best model fit. Results analysis will be examined for both treatment effects and the Treatment x Time Block interaction results.

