2. Subjects will report lower levels of craving as measured by the Visual Analog Scale (VAS) and the Alcohol Urge questionnaire (AUQ) during the exenatide Challenge Trial compared to the sham injection Challenge Trial.	Craving measures (AUQ and VAS) collected at 30-minute intervals during the self-administration trials will be used to test the effect of exenatide on alcohol craving. A mixed models approach will be used to test for differences in craving between the exenatide and sham injection Challenge Trials. Within-subject factors for this analysis will include Treatment and Time Block. Trial order will be used as covariate in these analyses to allow evaluation as to whether the order of treatments has a significant effect on the outcome.
Hypothesis 3: Areas under the breath alcohol concentration curves (AUC's) in heavy drinkers obtained during the first 40 minutes after ingestion of the priming drink of alcohol will be significantly lower in subjects when they receive exenatide as compared to when they are given sham injections	AUC's for BAC obtained using data obtained during the 40-minute absorption period will be compared between Challenge Trials using a repeated measures mixed models approach. In addition, individual BAC values obtained at 10-minute intervals after alcohol ingestion of the priming drink also will be compared between the sham injection and exenatide treatment trials using a repeated measures mixed models approach. A significant time x trial interaction value also will be taken to indicate a significant between trial difference in the rates of alcohol absorption.
Hypothesis 4. The proportion of subjects with post-trial blood glucose levels in the hypoglycemic range will not differ significantly between the sham injection and exenatide trials.	The proportion of subjects with blood glucose values below 50 mg/dl will be compared within subjects using the McNemar's test. We hypothesize that there will be no difference in blood glucose levels between the alcohol Challenge Trials.

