	Baseline (May be split over 2 visits)	Randomization & Trial1	Trial 2
Clinic Visit #	0	1	2
COVID-19 Screening Questionnaire (pre-visit)	X	X	X
Informed Consent	X		
Urine Drug Screen ^A	X	X	X
Locator Form	X		
Demographics	X		
Medical History	X		
Physical Exam	X		
MINI V 6.0	X		
CBC w Diff AST, ALT, GGT, Tbili, BUN, Ca, CO2, Cl, Cr, G K, Na, Triglycerides, Serum lipase, Ha1c	X		
Vital Signs, weight, Blood Alcohol Level ^{b, c}	X	X	X
ECG	X		
Prior and Concomitant Meds	X	X	X
CIWA-AR	X	X	X
Eligibility Checklist		X	
Confirm Eligibility to continue		X	X
Urine Pregnancy Test	X	X	X
Birth control assessment	X	X	X
AEs	X	X	X
C-SSRS	X	X	X
Treatment Referral			X
TLFB (28 day at baseline)	X	X	X
Alcohol Craving VAS ^c		X	X
OCDS ^c	X	X	X
AUQ ^c		X	X
Nausea VAS		X	X

The Effects of Exenatide, a GLP-1 Agonist, on Alcohol Self-Administration in Heavy Drinkers
Version 1.8 10.5.20

	Baseline (May be split over 2 visits)	Randomization & Trial1	Trial 2
Clinic Visit #	0	1	2
Blood Glucose (at end of block2)		X	X

A) Test for opioids, cocaine, amphetamines, methamphetamine, tetrahydrocannabinol (THC), barbiturates, oxycodone, buprenorphine, methadone and benzodiazepines, and alcohol (Ethyl Glucuronide)
B) if the baseline visit is split between two days, vitals, breathalyzer, and weight are to be taken at each visit.
c) See Table 2 for specific administration times

Items highlighted in blue will be performed in-clinic remote. The study staff and subject will connect through video call while located in separate rooms in the Clinical Studies Unit to avoid unnecessary face-to-face contact. Forms that must be filled out by the subject will be left on a clipboard in the exam room to be occupied by the subject, and study staff will instruct subjects to fill out the forms. Forms filled out by study staff through interviewing the subject will be kept in the study staff's room. The COVID-19 screening questionnaire will be administered before the subject arrives for their in-clinic visit.

Items highlighted in yellow will be performed with social distancing. The study staff and subject will be located in the same room, but will maintain a 6-foot distance and both persons will wear PPE at all times.

Items highlighted in green require direct contact between study staff and subject. Contact will be limited to minimum necessary and PPE will be worn at all times by both study staff and subject.

The Effects of Exenatide, a GLP-1 Agonist, on Alcohol Self-Administration in Heavy Drinkers

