Version 1.8 10.5.20

16. Appendix B: Schedule of assessments during drinking lab

	Pre-challenge	Observation	Self-admin Block1	Self-admin Block2
Assessment				
BAC	Prior to drug admin	Every 10 minutes	Every 30 minutes	Every 30 minutes
VAS-Alcohol Craving	Prior to drug admin	Every 10 minutes	Every 30 minutes	Every 30 minutes
AUQ	Prior to drug admin	At end of observation	Every 30 minutes	Every 30 minutes
OCDS	Prior to drug admin	None	None	None
VAS-Nausea			End of block	End of block

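### The craving models give no role to the pre-drug VAS and AUQ scores scheduled at each Challenge Trial; adjusting could sharpen the Treatment effect if between-trial differences in pre-drug and in-block craving correlate above about 0.20

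*Combined protocol and SAP*

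**What the plan says.** Section 4.2.1 makes craving a primary outcome: "The primary outcomes are alcohol consumption and cravings during the alcohol self-administration trials". For Hypothesis 2, section 12.1 states: "Craving measures (AUQ and VAS) collected at 30-minute intervals during the self-administration trials will be used to test the effect of exenatide". The factors are Treatment and Time Block, and the only covariate is described thus: "Trial order will be used as covariate in these analyses to allow evaluation as to whether the order of treatments has a significant effect". Section 9 (Alcohol self-administration Blocks 1 and 2) describes the same in-block readings: "Cravings will be assessed using the AUQ and VAS every 30 min during the self-administration blocks".

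The appendices schedule more than this. Appendix A marks the "Alcohol Craving VAS" row and the AUQ row at both Trial 1 and Trial 2. In Appendix B, the Pre-challenge entry for both the "VAS-Alcohol Craving" row and the AUQ row is "Prior to drug admin". Each subject who completes both trials should therefore have two pre-drug scores on each scale. No section says how they will be used.

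Section 12.2 sizes the trial on alcohol consumed (28 completers). It gives no SD, effect size or power for craving.

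**The concern.** A crossover removes stable differences between subjects. It does not remove differences between a subject's two visits that are already present before the injection, such as arriving with stronger craving on one day. These stay in the within-subject error of the treatment comparison. The pre-drug VAS and AUQ measure exactly this, and they are already on the schedule.

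What is at stake is the width of the craving confidence interval. The trial was not sized for craving, and section 12.1 may reduce the analysed number further: "data from subjects who experience moderate to severe nausea during the alcohol self-administration trials will be excluded from our statistical analysis". Timing matters too. A covariate added to a primary-outcome model after unblinding would look chosen for its result, so the decision is only clean if made beforehand.

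**Working it through.** **The plan's own figure.** There is none for craving. For consumption, section 12.2 gives effect size 0.7, alpha 0.01, 28 completers and power 0.81. A two-sided paired t-test with these inputs has power 0.815 (0.813 on 26 df, after a trial-order term), so the stated figure reproduces.

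**Inputs for craving.** n = 28 completers (section 12.2). n = 24 and n = 20 are assumed, to show the effect of nausea exclusions. r is not in the documents, so a range is used.

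**Definition of r.** For each subject, D_Y is the exenatide-minus-sham difference in in-block craving and D_X is the same difference in pre-drug craving; r is the correlation of D_Y with D_X across subjects. It is not the raw within-visit correlation. If both scores have the same intraclass correlation ICC, and rho_B is the between-subject correlation, then r = (raw − rho_B × ICC)/(1 − ICC). With assumed values ICC = 0.5, rho_B = 0.5 and raw correlation 0.2, r = (0.2 − 0.25)/0.5 = −0.1.

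**Variance ratio.** Compare the regression of D_Y on intercept and order with the same regression plus D_X. The expected variance ratio for the treatment effect, adjusted to unadjusted, is (1 − r²) × (1 + 1/(n − 4)). Setting it to 1 gives the break-even r = √(1/(n − 3)).

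At n = 28 the second factor is 1 + 1/24 = 1.0417. At r = 0.3 the ratio is 0.91 × 1.0417 = 0.948. Break-even is √(1/25) = 0.200.

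| n | break-even r | r = 0 | r = 0.2 | r = 0.3 | r = 0.5 | r = 0.7 |
|---|---|---|---|---|---|---|
| 28 | 0.200 | 1.042 | 1.000 | 0.948 | 0.781 | 0.531 |
| 24 | 0.218 | 1.050 | 1.008 | 0.956 | 0.788 | 0.536 |
| 20 | 0.243 | 1.062 | 1.020 | 0.967 | 0.797 | 0.542 |

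Simulation agrees: at n = 28 and r = 0, 0.2, 0.3, 0.5, 0.7 it gives 1.041, 0.998, 0.947, 0.779, 0.532.

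**Interval width at n = 28.** This is the square root of the variance ratio times the change in the t quantile from 26 to 25 df. At two-sided 0.05 it is 1.02, 1.00, 0.98, 0.89 and 0.73 at the same five values of r.

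**Power at n = 28, illustration only.** Take an assumed craving effect of 0.5 SD of the within-subject difference. At two-sided 0.05, power is 0.721 unadjusted and 0.703, 0.720, 0.743 and 0.820 adjusted, at r = 0, 0.2, 0.3 and 0.5. At two-sided 0.01 it is 0.461 unadjusted and 0.439, 0.458, 0.485 and 0.587 adjusted.

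**Change scores.** If D_X and D_Y have equal SDs, subtracting the pre-drug score gives a variance ratio of 2(1 − r): 2.00, 1.40, 1.00 and 0.60 at r = 0, 0.3, 0.5 and 0.7. This loses precision whenever r is below 0.5.

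**Treatment x Time Block.** This contrast compares blocks within a trial. A covariate that is constant within a trial cancels from it in balanced data, so the figures above apply to the Treatment main effect only.

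**The case against.** The strongest objection is that nothing here is broken. The planned model is a valid within-subject analysis, and adding a per-trial baseline is an efficiency preference. That stands.

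The gain is also undetermined in sign. The documents give no reason to expect a high r. Injection precedes the priming drink by 30 minutes; then come 5 minutes of drinking, 40 minutes of observation and two 60-minute blocks. The analysed readings therefore fall roughly 75 to 195 minutes after injection, with alcohol in between. For r from 0 to 0.3, interval width changes by only about 2% either way. That stands too, and it limits the point to a suggestion.

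A third objection concerns carry-over. In the exenatide-first sequence, the Trial 2 pre-drug score follows earlier exenatide exposure. If that exposure shifted the score by L but left in-block craving unchanged, adjustment would move the treatment estimate by (regression slope) × L/2. Section 9 gives a 7-14 day washout, clearance within 2 days and a 2.4-hour half-life. Carry-over is therefore unlikely on the protocol's own figures, but clearance alone does not exclude a behavioural effect.

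A reader might infer that the plan is biased, that any raw pre-drug/in-block correlation above 0.2 guarantees a gain, or that the pre-drug scores cannot be touched by treatment. The documents support none of these. The unadjusted contrast is unbiased, the threshold applies to correlated differences, and the Trial 2 score is treatment-free only if the washout is complete.

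**Conclusion.** The pre-drug craving scores are scheduled at both Challenge Trials and have no stated use in the Hypothesis 2 models; confidence in that is high. Confidence that adjustment would help is moderate, because it rests on an r that the documents do not supply.

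The trade-off is asymmetric. At n = 28 the expected loss is at most about 4% of variance (5-6% at n = 24 or 20). The gain is about 5% at r = 0.3 and 22% at r = 0.5, though nothing in the documents supports values as high as 0.5. These figures assume complete pairs and no carry-over into the Trial 2 pre-drug score.

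This is a low-cost improvement that the sponsor could make, not a defect that must be corrected.

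**What to change.** Before unblinding, add to the Hypothesis 2 text, separately for VAS and AUQ:

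- Include that trial's pre-drug score as a covariate, together with the subject's mean pre-drug score, so that only within-subject variation informs the adjustment.
- Enter trial order as period (Trial 1 or Trial 2). The present wording could also be read as treatment sequence. With period coding and complete data, the model equals regressing the exenatide-minus-sham difference on the pre-drug difference and order.
- For a subject with one trial only, use the single pre-drug score as the subject mean, so that the subject adds nothing to the within-subject baseline term.
- Do not analyse change from the pre-drug score.
- Keep the unadjusted model as a sensitivity analysis, mainly to guard against carry-over into the Trial 2 pre-drug score.

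If the sponsor expects r below about 0.2, one sentence stating that the pre-drug scores will not be used as covariates would also settle the matter. Either way the cost is analysis-plan wording: no new visits, measurements or subjects.

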4.2.2 Secondary Outcome Measures

A secondary aim of the present study is to examine the effects of exenatide on the absorption of

The Effects of Exenatide, a GLP-1 Agonist, on Alcohol Self-Administration in Heavy Drinkers
Version 1.8 10.5.20

alcohol in a sample of heavy drinkers. It is hypothesized that areas under the breath alcohol concentration curves in heavy drinkers obtained during the first 40 minutes after ingestion of the priming drink of alcohol will be significantly lower in subjects when they receive exenatide as compared to when they are given sham injections. Another secondary goal of this study will be to determine whether blood glucose levels enter into the hypoglycemic range in any of the study subjects receiving the combination of alcohol and exenatide. It is hypothesized that the proportion of subjects with post-trial blood glucose levels in the hypoglycemic range will not differ significantly between the sham injection and exenatide treatment trials.

5 Study Design

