There is a warning that post-marketing data indicate that acute pancreatitis including necrotizing pancreatitis and hemorrhagic pancreatitis (fatal and non-fatal) have occurred in association with exenatide administration. A precaution exists stating that there is an increased risk of hypoglycemia occurring in patients taking exenatide in combination with sulfonylureas. The administration of pharmacologic doses of GLP-1 were not found to increase the incidence of occurrence of hypoglycemia in fasting healthy subjects⁵⁷. Exenatide may produce nausea and vomiting that can be problematic in patients with impaired renal function. This drug was not well tolerated in patients with end-stage renal disease who were undergoing dialysis. It is advised that exenatide be used with caution in patients with severe renal impairment. Some reports of allergic reactions have been reported during post-approval use of exenatide including injection-site reactions, generalized pruritus and/or urticaria, macular or papular rash, angioedema, anaphylactic reaction.

In a study of the effects of monotherapy with exenatide 10 mcg twice daily over a period of 24 weeks, 10% of subjects experienced nausea vs 0% of those who received placebo. Three percent of subjects vomited vs. 0% of those who received placebo⁵⁸. In one study 65% of healthy subjects developed nausea following injection of 10 mcg dose exenatide when they were allowed to eat a standardized meal 60 minutes after the administration of this drug⁵⁹. In a dose ranging study of exenatide monotherapy with type-2 diabetics, nausea was reported by 13% of subjects receiving .1 mcg/kg dose, 0% of subjects receiving .2 mcg/kg dose, 29% of subjects receiving .3 mcg/kg dose, 60% of subjects receiving .4 mcg/kg dose, and 14% of subjects receiving placebo⁶⁰. There is a warning that thyroid C-cell tumors have been observed to occur in female rats receiving extended release treatment with exenatide. Also, exenatide has produced developmental toxicity when administered to pregnant rats.

Table 3. Combination therapy vs. placebo		
Adverse effect	Placebo	Combination Therapy
Nausea	18%	44%
Vomiting	4%	13%
Diarrhea	6%	13%
Feeling jittery	4%	9%
Dizziness	6%	9%
Headache	6%	9%
Dyspepsia	3%	6%
Asthenia	2%	4%
Gastric Reflux	1%	3%
Hyperhidrosis	1%	3%

Risks of Phlebotomy, medication injection, and pinprick for blood glucose test

These procedures may cause pain, bruising, lightheadedness, fainting and on rare occasions, infection.

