12.2 Sample Size Determination

A group size of 28 completers was selected for use in this study based on an assumed effect size of 0.7 suggested by similar alcohol self-administration studies with amount consumed as the primary outcome^{42,44}. This effect size is in the range we found for the anticonvulsant zonisamide used in a similar alcohol self-administration study⁴³. The sample size for this study is based on an estimated reduction of 1.5 standard drinks with an estimated standard deviation (2.1) of the between Challenge Trial differences in alcohol self-administration, with an effect size

The Effects of Exenatide, a GLP-1 Agonist, on Alcohol Self-Administration in Heavy Drinkers
Version 1.8 10.5.20

of this magnitude (i.e. 0.7). This requires a sample size of 28 to allow for detection of a significant within-subject difference in alcohol consumption with an alpha value of 0.01 and power value of 0.81. Based on an estimated 15-20% rate of non-completion for randomized subjects, we anticipate randomizing 36 subjects to achieve a sample of 28 completers. Given our experience with recruiting AUD populations into clinical trials, we expect a screening exclusion rate of roughly 50%. Approximately 72 subjects will be consented and screened in clinic to yield a sample of 36 eligible subjects.

Given that this a laboratory based experiment we do not plan to conduct any planned interim analyses in this study.

13 Ethics/Protection of Human Subjects

This study is to be conducted according to applicable US federal regulations and institutional policies (which are based in federal regulations, guidance, and ICH Good Clinical Practice guidelines).

This protocol and any amendments will be submitted to the Boston Medical Center and Boston University Medical Campus IRB, for formal approval of the study conduct. The decision of the IRB concerning the conduct of the study will be made in writing to the investigator. A copy of the initial IRB approval letter will be provided to the sponsor before commencement of this study.

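### Hypothesis 4 (hypoglycemia) is fulfilled by a non-significant McNemar test in about 28 pairs, with no margin or interval, and its cut-off differs from the one the procedures call hypoglycemic

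*Combined protocol and SAP*

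**What the plan says.** Section 4.2.2 sets a secondary goal of finding out "whether blood glucose levels enter into the hypoglycemic range in any of the study subjects" receiving exenatide with alcohol. It then hypothesizes that the proportion in that range "will not differ significantly between the sham injection and exenatide treatment trials". It gives no numeric threshold.

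Section 12.1, Hypothesis 4, repeats the hypothesis and gives the analysis: "The proportion of subjects with blood glucose values below 50 mg/dl will be compared within subjects using the McNemar's test". It adds: "We hypothesize that there will be no difference in blood glucose levels between the alcohol Challenge Trials". It does not state alpha, sidedness, exact or asymptotic version, confidence interval or margin.

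Section 12.2 sizes the study at 28 completers "to allow for detection of a significant within-subject difference in alcohol consumption with an alpha value of 0.01" and power 0.81. Nothing in that section concerns glucose.

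Section 9 (Alcohol self-administration Blocks 1 and 2) takes one planned reading at the end of Block 2 and says: "If the subject is found to be hypoglycemic (glucose < 70 mg/dL), staff will give the subject orange juice".

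**The concern.** Four things are wrong, in descending order of weight.

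1. The hypothesis is the null. A p-value above alpha agrees with it whether the data rule out an excess or merely fail to show one. No text says outright that non-significance proves safety, but Section 12.1 offers no other rule for reading the result.
2. The same label carries two cut-offs. A subject at 50 to 69 mg/dl is hypoglycemic in the procedures and a non-event in the analysis, and no text explains this.
3. The goal in Section 4.2.2 is to learn whether any subject enters the range. Counts with an interval answer that; a significance test does not. Section 12.1 plans no such count.
4. Section 12.1 also predicts no difference in glucose levels, but the only analysis is of the dichotomy.

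Section 6.1 acknowledges that the joint effect of GLP-1 agonists and alcohol on glucose is inadequately studied in humans, so this outcome is one of the few data points the study will yield on it. A report of no significant difference could be taken as reassurance that the data cannot give, in a study meant to support later phase II work (Section 4.1).

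**Working it through.** **Inputs.** From the documents: 28 completers (Section 12.2), one end-of-Block-2 reading per Challenge Trial (Section 9), and an event defined as glucose below 50 mg/dl (Section 12.1). The nausea exclusion in Section 12.1 covers primary outcomes only, so it removes no pairs here. The event rates, the alpha and the test version are not in the documents and are assumed below, with ranges.

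**The plan's own figure.** A two-sided paired t-test with effect size 0.7, alpha 0.01 and n = 28 has power 0.815, against 0.81 stated, and 28 is the smallest n that reaches 0.81. The sample size is therefore reproduced for drinking. It has no bearing on Hypothesis 4.

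**Step 1: what the test needs.** McNemar's test uses only discordant pairs. Let b be the number with an event on exenatide only and c the number with an event on sham only.

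- Exact: p = 2·P(Bin(b+c, 0.5) ≤ min(b, c)); for k:0 this is 2·0.5^k.
- Uncorrected: (b−c)²/(b+c) on 1 df; for k:0 the statistic is k.
- Continuity-corrected: (|b−c|−1)²/(b+c); for k:0 it is (k−1)²/k.

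| Split k:0 | Exact p | Corrected p | Uncorrected p |
|---|---|---|---|
| 4:0 | 0.125 | 0.134 | 0.0455 |
| 5:0 | 0.0625 | 0.074 | 0.025 |
| 6:0 | 0.031 | 0.041 | 0.014 |
| 7:0 | 0.0156 | 0.023 | 0.0082 |
| 8:0 | 0.0078 | 0.013 | 0.0047 |

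At 0.05 the exact and corrected tests need 6:0, and the uncorrected test needs 4:0. At 5:0 the unstated version alone decides whether the hypothesis is met.

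**Step 2: power with no sham events, two-sided alpha 0.05.** The number of exenatide events X is Bin(28, p). Power is P(X ≥ 6) for the exact or corrected test and P(X ≥ 4) for the uncorrected test.

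| True exenatide rate | Exact or corrected | Uncorrected |
|---|---|---|
| 5% | 0.2% | 4.9% |
| 10% | 5.5% | 31% |
| 15% | 23.5% | 62% |
| 20% | 50% | 84% |

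A 10-point excess is missed with probability 1 − 0.305 = 69% to 1 − 0.055 = 94%.

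**Step 3: sensitivity to the assumptions.**

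- Sham 5%, exenatide 15%, independent within subject: the discordant probabilities are 0.15 × 0.95 = 0.1425 and 0.05 × 0.85 = 0.0425. Summing the trinomial gives power 8.3% (exact or corrected) and 22% (uncorrected).
- Alpha 0.01, the only alpha in the documents and stated for drinking: exact needs 8:0 and uncorrected 7:0. Power at 10% against 0% is 0.5% and 1.8%.
- All 36 randomized subjects giving pairs, alpha 0.05, 10% against 0%: power 14.5% (exact) and 49% (uncorrected).

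**Step 4: what 28 subjects can exclude.** These are Clopper-Pearson two-sided 95% limits on the exenatide proportion. For 0/28 the upper limit is 1 − 0.025^(1/28) = 12.3%. For 1/28 it is 18.3% and for 2/28 it is 23.5%. For 5/28 (17.9%) the interval is 6.1% to 36.9%.

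**The case against.** This is a secondary outcome and no decision in the documents depends on the McNemar result. The stopping rules in Section 10.4 use serious adverse events and intoxication, and individual glucose is checked and acted on at the visit. Hypotheses 2 and 3 also lack alpha and power, and sizing a small laboratory crossover on one outcome is ordinary. Events may well be rare: diabetes is excluded, the mixer is chosen for this purpose ("Drinks will be mixed with a sugary mixer (3:1 Mixer:Alcohol) to preclude the occurrence of hypoglycemia"), and Section 6.1 reports that pharmacologic doses of GLP-1 "were not found to increase the incidence of occurrence of hypoglycemia in fasting healthy subjects". The power figures therefore rest on event rates that the documents do not supply. The sentence on glucose levels may be loose wording for the proportion. Two cut-offs can serve two purposes, one to trigger a procedure and one to define an analysis category.

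Much of this stands, and it limits the weight of the point. The power table is illustrative, the levels sentence may need only a drafting correction, and participant safety does not hang on this test. Three things survive. What is particular to Hypothesis 4 is not the missing power but that the null is the hypothesis. Rarity of events makes the test less informative, and the limits in Step 4 need no assumed event rate. If the cut-offs serve different purposes, no text says so, and both carry the same label. The descriptive goal in Section 4.2.2 would offer another reading, but it has no threshold and no matching analysis in Section 12.1.

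**Conclusion.** The concern holds. Following Section 12.1 exactly would count 5 of 28 against 0 of 28 as agreeing with a safety hypothesis under the exact or corrected test, although that result is compatible with an exenatide rate of up to 36.9%. With few events the planned test carries little information in either direction. The size of the shortfall depends on assumed rates, alpha and test version. At 10% against 0% it runs from a 69% to a 94% chance of missing the difference at alpha 0.05. The mismatch between below 50 and below 70 mg/dl is a plain inconsistency and rests on no assumption. The plan should be changed on this point, but the primary analysis and the sample size are unaffected.

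**What to change.** - Restate Hypothesis 4 as estimation: the number of subjects in the hypoglycemic range in each Challenge Trial, and the paired difference in proportions with an exact 95% confidence interval. Name the interval method in advance, since more than one exists.
- State that a p-value above alpha will not be reported as showing no difference. Any claim of no excess should rest on an upper confidence limit set against a margin stated and clinically justified beforehand.
- If McNemar's test is kept, give its version, sidedness and alpha.
- Either reword the sentence on glucose levels or support it with the paired mean difference in end-of-Block-2 glucose and its interval. Read that as an overall treatment effect, because alcohol and sugary mixer intake may differ between the two Challenge Trials.
- Reconcile the thresholds in Sections 9 and 12.1, or label each explicitly with its purpose, and carry the definition into Section 4.2.2. This review takes no view on which cut-off is right.

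The cost is wording, plus the clinical justification of a margin if a no-excess claim is wanted. The readings are already collected in both Challenge Trials. The safety statement becomes weaker: the upper limit on the exenatide proportion is 12.3% with no events in 28, and each event raises it. That limit is for the single proportion; the interval for the paired difference must be computed separately.
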